3.1.1.2. Systemic Events (Systemic Event Symptoms and Fever)

The systemic events assessed and recorded in the e-diary are fever, decreased appetite, drowsiness/increased sleep, and irritability from Day 1 through Day 7, where Day 1 is the day of each dose. The derivations for systemic events will be handled similarly to the way local reactions are handled for severity level, duration, and onset day (see Section 3.1.1.1).

The systemic events of decreased appetite, irritability, and drowsiness/increased sleep will be assessed by participant's parent(s)/legal guardian(s) as mild, moderate, or severe according to the grading scale in Table 3. Grade 4 will not be collected in the e-diary but will be collected as an AE on the CRF.

Table 3. Grading Scales for Systemic Events

Systemic Event	Mild	Moderate	Severe	
	Grade 1	Grade 2	Grade 3	Grade 4 ^a
Decreased appetite	Decreased	Decreased oral	Refusal to feed	Emergency room visit or
(loss of appetite)	interest in eating	intake		hospitalization for severe
				decreased appetite (loss of
				appetite)
Drowsiness	Increased or	Slightly subdued	Disabling not	Emergency room visit or
(increased sleep)	prolonged	interfering with	interested in usual	hospitalization for severe
-	sleeping bouts	daily activity	daily activity	drowsiness (increased sleep)
Irritability	Easily consolable	Requiring	Inconsolable;	Emergency room visit or
(fussiness)		increased	crying cannot be	hospitalization for severe
		attention	comforted	irritability (fussiness)
(synonymous with				
restless sleep;				
decreased sleep)				

Abbreviation: CRF = case report form.

Maximum temperature range over the period from Day 1 through Day 7 will be mapped into the ranges described in Table 4 for summary of maximum temperature. Fever will be grouped into ranges for the analysis according to Table 4.

Table 4. Ranges for Fever

≥38.0°C to 38.4°C	
>38.4°C to 38.9°C	
>38.9°C to 40.0°C	
>40.0°C	

Note: Fever is defined as temperature ≥ 38.0 °C.

a. Grade 4 assessment should be made by the investigator. Grade 4 will not be collected in the e-diary but will be collected as an AE on the CRF.

3.1.1.4. Adverse Events

AEs will be categorized according to MedDRA terms. AEs will be assessed from the time of informed consent through 1 month after the last assigned vaccination.

The primary endpoint "AEs from vaccination through 1 month after the last assigned vaccination" and other supportive AE endpoints will be summarized by SOC and PT on a participant level.

This primary endpoint will be supported by summaries and listings of related AEs, severe AEs, and immediate AEs (within the first 30 minutes after each dose).

AE reporting will be based on the specific reporting period. Missing AE start dates will be imputed following the Pfizer data standard rules as described in Section 5.3.

A 3-tier approach will be used to summarize AEs from vaccination through 1 month after the last assigned vaccination. Under this approach, AEs are classified into 1 of 3 tiers. Different analyses will be performed for different tiers (see Section 6.1.1.3.1). The control group for both the 1-dose and 2-dose 20vPnC groups (after the last assigned dose) is the 13vPnC group.

- Tier 1 events: These are prespecified events of clinical importance and are identified in a list in the product's Safety Review Plan. No Tier 1 events have been identified to date for 20vPnC.
- Tier 2 events: These are events that are not Tier 1, but are "common." A MedDRA PT is defined as a Tier 2 event if there are at least 4 participants with the AE term in at least 1 vaccine group.
- Tier 3 events: These are events that are neither Tier 1 nor Tier 2.

3.1.1.5. Serious Adverse Events

SAEs will be categorized according to MedDRA terms. SAEs will be collected from the signing of the ICD through the end of the study.

3.1.2. Primary Pneumococcal Immunogenicity Endpoints

• Pneumococcal serotype-specific IgG concentration 1 month after the last dose.

Concentrations of anticapsular IgG for the 7 additional serotypes (8, 10A, 11A, 12F, 15B, 22F, and 33F) will be determined in all participants at 1 month after the last assigned vaccination using the Luminex assay. Results will be reported as IgG concentrations.

To support the primary pneumococcal immunogenicity estimands, IgG concentrations for the 7 additional serotypes will be classified based on a serotype-specific IgG reference concentration of $0.35~\mu g/mL$.

3.2. Secondary Endpoints

• Pneumococcal serotype-specific IgG concentration 1 month after the last assigned vaccination.

To support the secondary pneumococcal immunogenicity estimands, IgG concentrations for the 13 matched serotypes will be classified based on serotype-specific IgG reference concentrations of 0.35 μ g/mL, except for 0.23 μ g/mL for serotype 5, 0.10 μ g/mL for serotype 6B, and 0.12 μ g/mL for serotype 19A.

• Pneumococcal serotype-specific OPA titers 1 month after the last assigned vaccination.

OPA titers will be determined in a random subset of participants from each vaccine group. Further details of the subsetting will be described in a memo to the unblinded statistical team before any testing proceeds.

3.4. Baseline Variables

Measurements or samples collected prior to Dose 1 are considered the baseline data for the assessments.

3.4.3. Prior/Concomitant Vaccines and Concomitant Medications

Other vaccines licensed and recommended for this age group may be administered as specified in the protocol. Concomitant medications will be recorded only if they were used to treat SAEs. Concomitant and prior vaccines and concomitant medications will be coded using the WHO Drug Dictionary.

Participants' time since the last 13vPnC vaccination will be calculated.

3.5. Safety Endpoints

Local reactions, systemic events, AEs, and SAEs have been described above in the Primary Endpoints section.

4. ANALYSIS SETS (POPULATIONS FOR ANALYSIS)

Analysis populations are defined for the statistical analysis of safety and immunogenicity results in the table below.

Population	Description	
Enrolled	"Enrolled" means all participants who sign the ICD.	
Randomized	All participants who are assigned a randomization number in the IWR system.	
Evaluable immunogenicity	 All participants who: Are eligible, Receive vaccinations to which they were randomized, Have at least 1 valid immunogenicity result from 1 month after the last assigned vaccination collected within 27 to 56 days after the dose, and 	

Population	Description	
	4. Have no other major protocol deviations as determined by the clinician	
	The evaluable immunogenicity population will be used as the primary analysis population for the pneumococcal immunogenicity results. Participants will be grouped according to the vaccine as randomized in the analysis based on the evaluable immunogenicity population.	
	CCI	
Safety	All participants who receive at least 1 dose of the study intervention and have safety data reported after any dose. Participants will be grouped according to the vaccine as administered in the analysis based on the safety population.	

For the evaluable immunogenicity population definition, the blood collection window has been expanded by 1 extra day before and 14 days after the protocol-specified blood collection window of 28 to 42 days defined in the protocol, for consistency with established rules in the Prevenar 13® development program. A major protocol deviation is a protocol deviation that, in the opinion of the Pfizer clinician or medical monitor, would materially affect assessment of immunogenicity, eg participant receipt of a prohibited vaccine or medication that might affect immune response, or a medication error with suspected decrease in potency of the vaccine.

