7. DISCONTINUATION OF STUDY INTERVENTION AND PARTICIPANT DISCONTINUATION/WITHDRAWAL

7.1. Discontinuation of Study Intervention

It may be necessary for a participant to permanently discontinue study intervention. Reasons for permanent discontinuation of study intervention include the following: AEs, participant's parent(s)'/legal guardian(s)' request, investigator request, and protocol deviation (including no longer meeting all the inclusion criteria, or meeting 1 or more exclusion criteria).

Note that discontinuation of study intervention does not represent withdrawal from the study. If study intervention is permanently discontinued, and the participant's parent(s)/legal guardian(s) consents, the participant will remain in the study and AEs and SAEs will be collected for 1 month after the last (most recent) study vaccination. See the SoAs ([Section 1.3.1](#) and [Section 1.3.2](#)) for data to be collected at the time of discontinuation of study intervention and follow-up for any further evaluations that need to be completed.

In the event of discontinuation of study intervention, it must be documented on the appropriate CRF/in the medical records whether the participant is discontinuing further receipt of study intervention or also from study procedures, postvaccination study follow-up, and/or future collection of additional information.

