9.1. Statistical Hypotheses

9.1.1. Estimands

The primary objectives of the study are to describe the safety profile and immune response to 1 or 2 doses of 20vPnC in healthy toddlers (≥ 12 to < 24 months of age) who received 2 infant doses of Prevenar 13. Estimands to address the study objectives are provided in [Section 3](#).

For estimands to evaluate the immunogenicity objectives, these estimands estimate the immune response in the hypothetical setting where participants follow the study schedule and protocol requirements. Immunogenicity results that are below the LLOQ will be set to $0.5 \times \text{LLOQ}$ in the analysis.

In the safety evaluation, missing e-diary data will not be imputed. Missing AE dates and missing AE severity will be imputed according to Pfizer safety rules. No other missing information will be imputed in the safety analysis.

Immunogenicity and safety results will be provided by descriptive summary statistics for each vaccine group. There is no formal hypothesis test for any safety or immunogenicity result.

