2.2. Study Objectives, Endpoints, and Estimands

Objectives	Endpoints	Estimands
Primary Safety Objective	Primary Safety Endpoints	Primary Safety Estimands
To describe the safety profile of 20vPnC	 Prompted local reactions (redness, swelling, and pain at the injection site) Prompted systemic events (fever, decreased appetite, drowsiness/increased sleep, and irritability) AEs SAEs 	In participants receiving at least 1 dose of study intervention with safety follow-up after the assigned vaccination: • The percentage of participants reporting prompted local reactions within 7 days after the last assigned vaccination in each group • The percentage of participants reporting prompted systemic events within 7 days after the last assigned vaccination in each group • The percentage of participants reporting AEs within 1 month after the last assigned vaccination in each group • The percentage of participants reporting SAEs within 1 month after the last assigned vaccination in each group
Primary Immunogenicity Objective	Primary Immunogenicity Endpoint	Primary Immunogenicity Estimand
To describe the immune responses to the additional 7 serotypes after 1 or 2 doses of 20vPnC	Pneumococcal serotype-specific IgG concentration	In participants complying with the key protocol criteria (evaluable participants) in each group: • Percentages of participants with predefined serotype-specific IgG concentrations for the 7 additional serotypes 1 month after the last assigned vaccination
Secondary Immunogenicity Objective	Secondary Immunogenicity Endpoints	Secondary Immunogenicity Estimands
To further describe the immune response of 20vPnC after 1 or 2 doses	 Pneumococcal serotype-specific IgG concentration Pneumococcal serotype-specific OPA titers 	 In evaluable participants in each group: IgG GMCs for the vaccine serotypes 1 month after the last assigned vaccination Percentages of participants with predefined IgG concentrations for the 13 matched serotypes 1 month after the last assigned vaccination OPA GMTs for the vaccine serotypes 1 month after the last assigned vaccination

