2.3. Study Design

This Phase 3, multicenter, randomized, partially double-blind study will be conducted at investigator sites in Europe.

Approximately 360 toddlers ≥12 to <24 months of age at the time of consent, who previously received 2 infant doses of 13vPnC (prior to 12 months of age), will be enrolled and randomized in a 1:1:1 ratio to receive either 1 or 2 doses of 20vPnC, or 1 dose of 13vPnC (control). The vaccine in toddlers randomized to receive 1 dose will be double-blind, as 20vPnC and 13vPnC have the same appearance and a single dose will be administered at Visit 1 of the study. Toddlers randomized to receive 1 dose are to return approximately 1 month later for Visit 2 for collection of safety information and a blood draw. For participants randomized to 2 doses of 20vPnC, the parent(s)/legal guardian(s) and site staff will know that these participants will need to return for a second vaccination visit and that they will receive 20vPnC at both Visit 1 and Visit 2 (approximately 2 months later), and after the second dose will return approximately 1 month later for Visit 3 for collection of safety information and a blood draw. The last assigned vaccinations will be the single vaccination at Visit 1 in the groups randomized to receive 1 dose of 20vPnC or 13vPnC (control) and the second vaccination given at Visit 2 in the group randomized to receive 2 doses.

Blood will be drawn from all participants for immunogenicity assessments before administration of the study intervention and 1 month after the vaccination (last vaccination in the group receiving 2 doses) in each vaccine group.

Participants will be observed for 30 minutes after each vaccination and any reactions occurring during that time will be recorded as immediate AEs. Prompted local reactions (redness, swelling, and pain at the 20vPnC or 13vPnC injection site), systemic events (fever, decreased appetite, drowsiness/increased sleep, and irritability), and use of antipyretic/pain medications occurring within 7 days after each vaccination will be collected via a provided

e-diary (or e-diary application). AEs and SAEs will be collected from the signing of informed consent to 1 month after the last dose.

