6.1.1.3. Adverse Events

6.1.1.3.1. Main Analysis

- Estimand: Proportions of participants reporting AEs.
- Analysis set: Safety population (Section 4).
- Analysis time point: Vaccination to 1 month after the last assigned vaccination (in the 2-dose group this will be the last vaccination to 1 month after the last assigned vaccination for reporting).
- Analysis methodology: Descriptive statistics.
- Reporting results: For all 3 tiers, the numerator (n) and the denominator (N) used in the percentage calculation, the percentage (%), and the corresponding 2-sided 95% CI for participants reporting any AE, each SOC, and each PT within each SOC will be presented by vaccine group.

In addition, for AEs classified as Tier 2 events, the differences in percentages and associated 2-sided 95% CIs for between-group comparisons (20vPnC - 13vPnC control) will be provided for each of the 20vPnC vaccine groups (the comparison will be the percentage from the last vaccination to 1 month after the last vaccination in the 2-dose group).

Further, for Tier 1 events, if any are identified, the difference in percentages, the associated 2-sided 95% CI for the risk difference, and the asymptotic p-values will also be provided.

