6.1.1.4. Serious Adverse Events

6.1.1.4.1. Main Analysis

- Estimand: Proportions of participants reporting SAEs.
- Analysis set: Safety population (Section 4).
- Analysis time point: Vaccination to 1 month after the last assigned vaccination (the last vaccination to 1 month after the last vaccination in the 2-dose group).
- Analysis methodology: Descriptive statistics.
- Reporting results: The numerator (n), and the denominator (N) used in the percentage calculation, the percentage (%), and corresponding 2-sided 95% CI will be presented for each vaccination group.

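### Does the broad Safety population leave the denominator for the 2-dose arm's post-Dose-2 AE and SAE percentages open?

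*SAP*

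**What the plan says.** The primary safety estimand (SAP 2.2, repeated from protocol section 3) applies "In participants receiving at least 1 dose of study intervention with safety follow-up after the assigned vaccination", and each of its four percentages is timed to the last assigned vaccination. SAP 2.3 fixes that vaccination as "the second vaccination given at Visit 2 in the group randomized to receive 2 doses"; in the other two arms it is the single dose.

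SAP 6.1.1.1 to 6.1.1.4 name the Safety population as the analysis set and add no condition. SAP section 4 defines that set as "All participants who receive at least 1 dose of the study intervention and have safety data reported after any dose". The set is grouped by the vaccine administered.

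The AE time point in SAP 6.1.1.3.1 carries a note: "in the 2-dose group this will be the last vaccination to 1 month after the last assigned vaccination for reporting". The Tier 2 clause in the same section says that "the comparison will be the percentage from the last vaccination to 1 month after the last vaccination in the 2-dose group". The SAE time point in SAP 6.1.1.4.1 has a similar note in brackets: "the last vaccination to 1 month after the last vaccination in the 2-dose group". Both sections report n and N for each percentage but do not say who makes up N.

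Protocol 7.1 covers a child who stops vaccination: with parental consent "the participant will remain in the study and AEs and SAEs will be collected for 1 month after the last (most recent) study vaccination". On missing data, protocol 9.1.1 states: "No other missing information will be imputed in the safety analysis". SAP 5.3 is to the same effect.

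**The concern.** The named analysis set is wider than the estimand population. A child randomized to 2 doses who stops after Dose 1 has safety data after a dose, so belongs to the Safety population, yet has no follow-up after Dose 2. Protocol 7.1 foresees such children. Three treatments can be imagined:

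- **Kept as a non-event.** The child stays in N with no AE, which lowers the 2-dose percentage.
- **Post-Dose-1 events counted.** The SAE note and the Tier 2 clause drop the word for assigned, so the last vaccination received might be taken as the start of the window.
- **Left out of N.** This matches the estimand.

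The choice would touch primary AE and SAE percentages and the Tier 2 differences against 13vPnC. It would act on one arm only, because in the single-dose arms the first dose is also the last. An AE can be the reason for stopping, so the affected children need not be a random subset.

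**Working it through.** **Reading the sections together**

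1. SAP 2.2 gives the condition (follow-up after the assigned vaccination) and the timing (last assigned). SAP 2.3 says this is Dose 2 in the 2-dose arm.
2. SAP 3.1.1 lists the AE and SAE endpoints as ending 1 month after the last assigned vaccination. SAP 3.1.1.4 names 13vPnC as the control for both 20vPnC groups and, for this comparison, specifies the period after the last assigned dose.
3. The two short forms in SAP 6.1.1.3.1 and 6.1.1.4.1 are bracketed notes to endpoints already defined that way. Using them to bring in post-Dose-1 events would set a shorthand against the definition. It would also be inconsistent, since the Dose 1 events of children who did go on to Dose 2 are outside the window.
4. Keeping the child as a non-event would assign an outcome to a period that was never observed, which fits poorly with the no-imputation statements.
5. For prompted events, SAP 6.1.1.1.1 and 6.1.1.2.1 tie the estimand to the last assigned vaccination, and protocol 9.1.1 says missing e-diary data are not imputed. Only AEs and SAEs remain open.

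**The plan's own figure**

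Protocol 9.5, Table 5 gives the probability of at least one AE among 120 as 1 − (1 − p)^120. For p = 1%, 2% and 5% this is 70.06%, 91.15% and 99.79%, which agrees with the printed 70.1%, 91.1% and 99.8%.

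**Size of the effect**

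Inputs: 120 per arm (protocol 9.5). Assumed, because the documents give no values: m children missing Dose 2, a 40% any-AE rate after Dose 2, a 5% rate for a single term, and a post-Dose-1 rate q of 20% to 60% in the children who stop. The value m = 15 is an outer case borrowed from the planned loss of 120 − 105 for immunogenicity, which is not a Dose 2 dropout figure.

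- Kept as a non-event: rate × (120 − m)/120.
- Post-Dose-1 events counted: [(120 − m) × 0.40 + m × q]/120.

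| m | Factor | 40% shows as | 5% shows as | Dose 1 events counted, q = 20% | Dose 1 events counted, q = 60% |
|---|---|---|---|---|---|
| 3 | 0.975 | 39.0% | 4.875% | 39.5% | 40.5% |
| 6 | 0.950 | 38.0% | 4.75% | 39.0% | 41.0% |
| 15 | 0.875 | 35.0% | 4.375% | 37.5% | 42.5% |

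For scale, the Clopper-Pearson 95% interval for 48/120 is 31.2% to 49.3%. The Miettinen-Nurminen 95% interval for 6/120 against 6/120 is −6.2 to +6.2 points, so a shift of 0.25 points in a 5% term (m = 6) cannot be seen.

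**If N is limited to children followed after Dose 2**

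With m = 6, Miettinen-Nurminen for 6/114 against 6/120 is −6.0 to +6.7 points, a width of 12.6 compared with 12.3. At a 2% rate, 1 − 0.98^114 = 90.01% and 1 − 0.98^113 = 89.80%, so the plan's statement of more than 90% holds for up to 6 missing.

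**The case for a change.** The best case for a change is that no sentence defines N for these percentages, although SAP 6.5.3.1 shows that the authors state a denominator when they want to. The no-imputation rule does not fully settle the matter, because a child with no AE record is ordinarily a non-event rather than a missing value. Protocol 9.5 uses all 120 per group for AEs after the last assigned vaccination. Grouping by vaccine administered does not say whether the number of doses counts. And with the window starting at Dose 2, the events of children who stopped after Dose 1, perhaps because of an AE, drop out of the primary table.

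Part of this stands: N is not put into words. The rest carries less weight. SAP 6.5.3.1 takes the whole group as denominator and says so, which if anything suggests that N elsewhere is specific to the calculation. The 120 in protocol 9.5 is a planning number. The missing rule on arm grouping is the same kind of unstated detail, and the estimand refers to the assigned vaccination. Post-Dose-1 AEs are collected under protocol 7.1, and SAP 3.1.1.4 mentions further supportive AE endpoints without listing them. In a document with redactions, the absence of a post-Dose-1 summary cannot be shown.

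**Conclusion.** This is a missing detail that analysts applying the stated estimand would fill sensibly, by limiting N for the 2-dose arm's AE and SAE percentages to children followed after Dose 2. No change to the plan is needed.

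If the children were instead kept in N, an assumed 40% rate would move by 1 to 2 points with 3 to 6 of 120 missing Dose 2, and by 5 points in the outer case of 15. Each of these results lies inside the exact 95% interval for 48/120. The real size is unknown because the documents give no Dose 2 dropout.

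SAP 5.1 rules out hypothesis tests and decision rules, so no conclusion turns on the choice. It would also be visible: N is printed beside each percentage, and SAP 6.5.2.1 tabulates receipt of each dose by randomized group. The conclusion rests on reading SAP 2.2, 2.3 and 3.1.1.4 as governing the shorter notes in SAP 6.1.1. That is the natural reading, although the opening line of the estimand says assigned rather than last assigned.
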